### **10.2 Statistical Analysis Plan Summary**

The analysis set for antiviral activity analyses will be the Full Analysis Set which includes subjects who were enrolled and received at least one dose of study drug and have naïve chronic genotype 1b HCV infection with non severe fibrosis.

Statistical analysis will be performed using Stata software (version 13; Stata-Corp, College Station, Tex., USA). All statistical tests will be two-sided and  $p < 0.05$  will be considered significant.

Qualitative variables will be described in terms of numbers and proportions.

Quantitative variables will be described in terms of numbers, mean  $\pm$  standard deviation or median [inter-quartile range] according to statistical distribution (normality studied using Shapiro-Wilk test).

Graphic representations will be complete presentations of results.

Sensitivity analyses will be considered to measure the possible impact of missing data on results and the more appropriate imputation method. For the analysis of post-baseline categorical efficacy endpoints, if a data point is missing and is immediately preceded and followed in time by values that are deemed successes, then the missing data point will be termed a success; otherwise the data point will be termed a failure. For example if a data point is missing and is preceded and followed in time by values that are <LLOQ target not detected (TND), then the missing data point will be set to < LLOQ TND.

Demographic and baseline measurements will be summarized using standard descriptive methods by treatment group and overall.

Exploratory analyses may be performed to assess the relationship between demographic, baseline characteristics, (including baseline viral load, age, sex, baseline ALT level, bodyweight, fibrosis score and additional endpoints as necessary) and antiviral activity (HCV RNA reduction, proportion of subjects with HCV RNA below the limit of quantification and target not detected at various time points during and following discontinuation of study drugs). Predictive factors of antiviral activities may be examined using regression type of analysis.

An interim SVR 12 Clinical Study Report (CSR) will be done because SVR12 is suitable as a primary end point for regulatory approval. SVR12 and SVR24 measurements were concordant in a large population of subjects with HCV infection who participated in clinical trials with various treatment regimens and durations (28). Since the protocol continues to Post Treatment Week 24 visit, then we provide a SVR 24 CSR which will be the final CSR.

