**Statistical Methods :**

The sample size estimation was performed according to the precision of 95% confidence interval of the primary outcome measured by the proportion of subjects with sustained viral response 12 weeks after cessation of treatment. Considering an efficacy at 96%, **n=120 patients** will be included in this study and will be able to obtain an exact 95% confidence interval with a lower bound greater than 91.5%, which could be considered as the minimal efficacy obtained in several works presented recently in literature.

The primary efficacy endpoint for the study is the proportion of subjects with SVR12 in all enrolled and treated subjects.

Secondary efficacy endpoints include SVR4 and SVR24, and the proportion of subjects with virologic failure.

Safety endpoints will be analyzed by the number and percent of subjects with events or abnormalities for categorical values or 8-number summary (n, mean, standard deviation, median, Q1, Q3, minimum, maximum) for continuous data.

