## 4. STUDY DESIGN

### 4.1 Trial Design

This is a multi-site, open-label evaluating the efficacy of GRAZOPREVIR (100 mg - second-generation protease inhibitor) in combination with ELBASVIR (50 mg - NS54A inhibitor), in treating non-cirrhotic, treatment-naïve (TN) subjects with chronic hepatitis C (CHC) infection with genotypes 1b to be conducted in conformance with Good Clinical Practice.

Approximately 120 subjects will be enrolled in this study.

There will be one treatment group with EBR/GZR (50/100 mg) once daily without regards to food for 8 weeks.

Several measures have been included in order to limit risk to the study subject.

- Subjects will be discontinued from all study therapy (where applicable) if they meet any of the criteria for discontinuation (details in Section 5.4).
- Study therapy will also be discontinued for subjects who meet criteria for virologic failure (defined in section 2.8.4).
- In the event there is an unacceptable rate of virologic failure (details in section 2.8.4) or discontinuation of study medications due to safety concerns, the treatment or the entire study may be terminated.

Specific procedures to be performed during the trial, as well as their prescribed times and associated visit windows, are outlined in the Trial Flow Chart - Table 7 Details of each procedure are provided in Section 8.1 – Trial Procedures.

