#### 5.4.1 Subject Replacement Strategy

A subject that discontinues from the trial will not be replaced except if the subject is a screen fail or wrongly included. The screen fail rate is estimated at around 20%, so we plan to include about

145 patients in the study (patient who signed the informed consent form).

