## **10. STATISTICAL ANALYSIS PLAN**

### **10.1 Sample size estimation**

To evaluate the efficacy of of Elbasvir/Grazoprevir Fixed-Dose Combination for 8 Weeks in Treatment-Naïve for HCV GT1b-Infected Patients, with non-severe fibrosis, the sample size estimation was performed according to the precision of 95% confidence interval of the primary outcome measured by the proportion of subjects with sustained viral response 12 weeks after cessation of treatment. Considering an efficacy at 96%, n=120 patients will be able to obtain an exact 95% confidence interval with a lower bound greater than 91.5%, which could be considered as the minimal efficacy obtained in several works presented recently in literature.

An exploratory interim analysis will be conducted. More precisely, we want to evaluate whether after the inclusion of the first 50 patients, the expected SVR12 rate of 96% always seems a robust and possible assumption. In order to better estimate the rate of responders treated and to ensure that with 120 patients the lower limit of the 95% confidence interval is well above 91.5%, it seems reasonable and relevant to consider early intermediate analysis, without inflation of type I error.

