### **10.3 Analyses for the primary outcome**

To evaluate the efficacy of Elbasvir/Grazoprevir Fixed-Dose Combination for 8 Weeks in Treatment-Naïve for HCV GT1b-Infected Patients, with non-severe fibrosis as measured by the proportion of subjects with sustained viral response 12 weeks after cessation of treatment (SVR 12), the proportion of patients presenting a sustained viral response 12 weeks after cessation of treatment (HCV RNA < LLOQ 12 weeks after cessation of treatment) will be presented with the associated 95% confidence interval estimated using binomial exact distribution (exact confidence interval). The lower-bound of the confidence intervals will be studied and analyzed regardless assumptions proposed for sample size estimation.

A detailed description of patients not assume SVR12 will be proposed according to clinical relevance using age, gender, BMI, fibrosis score, viral charge and additional endpoints as necessary

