### **10.4 Analyses for the secondary objectives**

Most of secondary analyses will be exploratory and will be performed as described previously (i) to evaluate the safety and tolerability of EBR/GZR treatment, (ii) to determine the proportion of subjects who attain SVR at 4 and 24 weeks after cessation of treatment (SVR4 and SVR24), (iii) to evaluate the proportion of subjects with virological failure and (iv) to evaluate the emergence of viral resistance to EBR/GZR during treatment and after cessation of treatment. Finally, to evaluate the kinetics of circulating HCV RNA during treatment and after cessation of treatment, a descriptive statistical analysis will be proposed. This analysis will be completed using random-effects models useful to evaluate kinetics taking into account between and within patient variability.

To better understand the potential for Resistance Associated Variants (RAVs) with EBR and/or GZR, samples will be retained from Day 1 and viral failure visits and RAVs will be assessed for any subject who has detectable virus above 1000 UI/mL and has met a virologic failure criteria. Subjects who discontinue the treatment will continue to participate in the scheduled follow-up activities including monitoring for resistance.

Exploratory IL28B genotyping may also be conducted to detect genetic variations associated with response to treatment of hepatitis C. A separate signature will be required to document a subject's agreement to provide additional samples for optional genetic research.

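### The primary analysis population is defined in two conflicting ways, and nothing requires exclusion or replacement of dosed patients to be decided on pre-dose data or blind to outcome

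*Combined protocol and SAP*

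**What the plan says.** **Denominator, synopsis (Statistical Methods).** "The primary efficacy endpoint for the study is the proportion of subjects with SVR12 in all enrolled and treated subjects". There is no eligibility condition.

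**Denominator, body.** Section 6.1.1 places the primary endpoint in the full analysis set. Section 10.2 defines that set as subjects who were "enrolled and received at least one dose of study drug and have naïve chronic genotype 1b HCV infection with non severe fibrosis".

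**Replacement.** Under section 5.4.1, a subject who discontinues "will not be replaced except if the subject is a screen fail or wrongly included". The section does not define a wrong inclusion, set a time limit, or say whether a replaced subject who was dosed is analysed.

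**When eligibility is settled.** The Day 1 procedures (8.1.5.2.1) include confirming eligibility, and 8.1.5.4 holds back drug assignment until all criteria are met. Genotyping, Fibroscan and Fibrotest are scheduled at screening only (section 7). Subtype is determined in local laboratories (8.1.3).

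**What is examined later.** Section 10.4 states that "RAVs will be assessed for any subject who has detectable virus above 1000 UI/mL and has met a virologic failure criteria". Section 10.3 plans a detailed description of patients without SVR12, with fibrosis score among the variables.

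**The fibrosis criterion.** Inclusion criterion 7 reads F ≤ 2 in the synopsis and F < 2 in section 5.1, with the same two test cut-offs in both places.

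**The concern.** In a single-arm trial the denominator is part of the result, because no control group undergoes the same exclusions. With two definitions in force, the population can be settled after the data are seen. The narrower definition depends on a judgement (does this patient have genotype 1b infection with non-severe fibrosis?) that the plan does not tie to pre-dose data, to a date, or to someone unaware of HCV RNA results. The trial is open label and section 10.1 plans a look at SVR12 after the first 50 inclusions, so outcomes will be known while such judgements could still be made.

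The planned later scrutiny (resistance testing and the descriptive review) falls on failures. If that scrutiny led to a finding of ineligibility, failures would leave the denominator more readily than responders, and SVR12 would be biased upwards.

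**Working it through.** **Inputs**
- n: "Approximately 120 subjects will be enrolled in this study" (4.1).
- Assumed SVR12 of 96% and a reference lower bound of 91.5% (10.1).
- Interval: exact binomial, 95% (10.3), taken as two-sided in line with 10.2: "All statistical tests will be two-sided".

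**Formula.** For x responders in n, the exact (Clopper-Pearson) lower limit is the 2.5% quantile of Beta(x, n − x + 1).

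**The plan's own figure first.** 0.96 × 120 = 115.2 responders, which is not a whole number.
- 115/120 = 95.8%: lower limit 90.5%.
- 116/120 = 96.7%: lower limit 91.7%.

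The stated bound above 91.5% is therefore reached only from 116 responders, that is, with at most 4 failures. The sample-size statement is a separate matter, but it shows that the planned result lies next to the benchmark.

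**Effect of the population, starting from 5 failures in 120**

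| Population | x/n | SVR12 | Exact 95% lower limit |
|---|---|---|---|
| All treated | 115/120 | 95.83% | 90.54% |
| One failure removed | 115/119 | 96.64% | 91.62% |
| That failure replaced by a responder | 116/120 | 96.67% | 91.69% |
| One ineligible responder removed instead | 114/119 | 95.80% | 90.47% |

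Removing a failure moves the limit up by 91.62 − 90.54 = 1.08 points. Removing a responder moves it down by 90.54 − 90.47 = 0.07 points. The rule can act in both directions, but very unequally.

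**How special is this case?** At a true SVR12 of 96%, the probability of exactly 5 failures is C(120,5) × 0.04⁵ × 0.96¹¹⁵ = 17.8%, and at least one of those 5 patients must also be judged ineligible. With 4 or fewer failures (probability 47.3%) the limit is above 91.5% anyway. With 6 failures, one removal gives 114/119 and 90.5%, so no crossing; two removals give 114/118 and 91.55%.

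**Range under an assumed removal share.** The documents give no misclassification rate. Suppose a share q of failures is removed and the sample is refilled to 120. The apparent response rate becomes p′ = p / [p + (1 − p)(1 − q)]. At a true p of 91.5%, the probability of at least 116 responders is:
- q = 0: 2.1%
- q = 10% (p′ = 92.3%): 4.1%
- q = 20% (p′ = 93.1%): 7.6%
- q = 30% (p′ = 93.9%): 13.7%

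At p = 91.5% about 120 × 0.085 = 10.2 failures are expected, so q = 10% corresponds to roughly one patient. These shares are illustrative.

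**The case against.** **Eligibility is settled before dosing.** Section 10.2 can be read as restating the inclusion criteria, which 8.1.5.2.1 and 8.1.5.4 require to be met before the first dose. No section sets up a later re-adjudication. This stands as a reason to expect few cases. It does not decide what happens to a case that does arise, or which denominator governs.

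**Section 5.4.1 is narrower than it may look.** It concerns subjects who discontinue, couples wrong inclusion with screen failure, and does not say that anyone leaves the analysis. A patient who completes treatment and relapses has not discontinued. This stands: a reader might infer that failures may be taken out and replaced under this section, but its text does not say so. Exclusion from the analysis would come from 10.2. What remains is the missing pre-dose limit and the silence about dosed subjects.

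**The route by which failures are found ineligible is inferred.** A reader might conclude that resistance testing would expose a wrong subtype only in failures. Section 10.4 mentions neither re-subtyping nor an eligibility check, and no fibrosis test is repeated. This objection stands, and the route is treated here as an assumption.

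**The direction is not fixed.** A reader might say that the restriction can only raise SVR12. It cannot be put that way, because an ineligible responder would also be dropped and the rate would fall slightly.

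**91.5% is not a decision rule.** Section 10.1 uses it to size the trial for precision, and 10.3 says that the bound will be interpreted irrespective of the sample-size assumptions. This stands. It is, however, the only numerical benchmark that the plan offers.

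**The restricted set matches the objective.** The objective concerns genotype 1b with non-severe fibrosis, so a set limited to those patients is defensible if membership is judged on pre-dose data. The plan does not require that.

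**Conclusion.** The plan is wrong as written, because its two primary populations cannot both apply. The conflict stands on the text alone. That removal of dosed patients would favour the treatment rests on the further assumption that ineligibility comes to light mainly in failures, which the documents neither state nor rule out. Nothing shows that such removal is intended.

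The effect is about 1 percentage point on the lower limit per failure removed, when there are 5 failures in 120. That is enough to move it from 90.5% to 91.6%, across the 91.5% benchmark. The crossing from a single removal needs exactly 5 failures, about an 18% chance at the assumed 96%, with one of them judged ineligible. It illustrates how sensitive the estimate is and does not predict what will happen. The differing fibrosis wording (F ≤ 2 and F < 2) adds to the uncertainty over who belongs in the section 10.2 set.

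**What to change.** 1. **Section 10.2:** define the primary Full Analysis Set as all enrolled subjects who received at least one dose, in agreement with the synopsis. Section 6.1.1 then needs no change.
2. **Section 5.4.1:** limit replacement to subjects not yet dosed, and state that every dosed subject stays in the primary analysis.
3. **Sensitivity analysis:** report SVR12 in the eligibility-restricted set. Judge eligibility only on pre-dose data, by someone blind to post-baseline HCV RNA, and list each exclusion with its reason and SVR12 outcome.
4. **Inclusion criterion 7:** reconcile the fibrosis grade between the synopsis and section 5.1.

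The cost is protocol and SAP wording plus one extra table. The reported SVR12 may be slightly lower if an ineligible patient was treated and failed.

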### **10.3 Analyses for the primary outcome**

To evaluate the efficacy of Elbasvir/Grazoprevir Fixed-Dose Combination for 8 Weeks in Treatment-Naïve for HCV GT1b-Infected Patients, with non-severe fibrosis as measured by the proportion of subjects with sustained viral response 12 weeks after cessation of treatment (SVR 12), the proportion of patients presenting a sustained viral response 12 weeks after cessation of treatment (HCV RNA < LLOQ 12 weeks after cessation of treatment) will be presented with the associated 95% confidence interval estimated using binomial exact distribution (exact confidence interval). The lower-bound of the confidence intervals will be studied and analyzed regardless assumptions proposed for sample size estimation.

A detailed description of patients not assume SVR12 will be proposed according to clinical relevance using age, gender, BMI, fibrosis score, viral charge and additional endpoints as necessary

### **10.4 Analyses for the secondary objectives**

Most of secondary analyses will be exploratory and will be performed as described previously (i) to evaluate the safety and tolerability of EBR/GZR treatment, (ii) to determine the proportion of subjects who attain SVR at 4 and 24 weeks after cessation of treatment (SVR4 and SVR24), (iii) to evaluate the proportion of subjects with virological failure and (iv) to evaluate the emergence of viral resistance to EBR/GZR during treatment and after cessation of treatment. Finally, to evaluate the kinetics of circulating HCV RNA during treatment and after cessation of treatment, a descriptive statistical analysis will be proposed. This analysis will be completed using random-effects models useful to evaluate kinetics taking into account between and within patient variability.

To better understand the potential for Resistance Associated Variants (RAVs) with EBR and/or GZR, samples will be retained from Day 1 and viral failure visits and RAVs will be assessed for any subject who has detectable virus above 1000 UI/mL and has met a virologic failure criteria. Subjects who discontinue the treatment will continue to participate in the scheduled follow-up activities including monitoring for resistance.

Exploratory IL28B genotyping may also be conducted to detect genetic variations associated with response to treatment of hepatitis C. A separate signature will be required to document a subject's agreement to provide additional samples for optional genetic research.

## **11. DIRECT ACCESS TO SOURCE DATA/DOCUMENTS**

### **11.1 Access to source data**

The sponsor shall be permitted to inspect the investigator center prior to commencement and during the course of the study to satisfy itself that the center is suitable and has the necessary facilities, staff and capacity to conduct the study. The investigator will ensure that his center has the necessary facilities, time and staff for conducting the study, and that these will be maintained for the duration of the study. The investigator will co-operate with the sponsor and any affiliated person to monitor or supervise the conduct of the study.

The study may be subjected to auditing by representatives of the sponsor and/or to inspection(s) by authorized representatives of local and/or foreign health authorities. In case of an audit or inspection, the investigator will be informed in advance.

The CRFs are to be made available for review by the clinical monitor or auditor or national regulatory inspectors. The investigators are required to give access to all source documents and study data in accordance with laws and regulations (articles L.1121-3 and R.5121-13 of the code of public health). The sponsor will not require the investigator or any member of their staff to take any action or be a party to any action which is contrary to the laws of the country in which the study is being carried out or to medical ethics.

### **11.2 Source documents**

The investigator agrees to allow direct access to source data of the study during monitoring visits, audits or inspections by authorized representatives of local and/or foreign health authorities. Source documents (medical records, the original results of laboratory test ...) are defined as any document proving the existence or the accuracy of a data or a registered event during the clinical study. It will be archived for 15 years by the investigator.

### **11.3 Confidentiality**

In accordance with GCP and with the national data protection laws, all information concerning the subjects in the study must be treated as strictly confidential by all persons involved in the study including the clinical, medical and statistical monitor.

The investigator acknowledge that any information acquired from the sponsor or developed or acquired in connection with the study are strictly confidential and that they will not be disclosed to any third party nor use them for any purpose without first obtaining the written consent of the sponsor.

People involved in the study and investigators themselves are subject to professional secrecy (under the conditions defined by Articles 226-13 and 226-14 of the Penal Code).

Such consent shall be deemed to have been given for disclosure to any person for whom the investigator is responsible at his centre, but only so far as required for the purposes of the study, and, in the case of disclosures to staff, only if such staff are bound by obligations of confidentiality no less strict than those set out herein.

### **11.4 Archiving**

The investigator must retain the subject identification codes for at least 15 years after completion or discontinuation of the study. Subject files and other source data must be kept for the maximum period of time permitted by the hospital, institution or private practice, but not less than 10 years, to meet international registration requirements. The investigator must produce them or supply copies thereof to the sponsor or to the regulatory authorities upon demand, whilst ensuring subject confidentiality at all times.

## **12. QUALITY CONTROL AND QUALITY ASSURANCE**

The CRFs, containing all the clinical information, will be carefully checked both by the Investigators and the Monitors against the source documents according to the Good Clinical Practices Guideline (CPMP/ICH/135/95).

